The number of outbreaks per arm will be collected from VESUV. At the start of the evaluation period, we will ask participating hospitals to submit the number of full-time positions per included ward. The number of inpatients per ward per day will be obtained from NPR. The number of positions and inpatients will be used as denominators when estimating the secondary attack rate in outbreaks. The number of patients registered in NOIS will be compared to the number of daily inpatients registered in NPR. If the number of inpatients per day changes over time, we will make a new collection of the number of full-time positions to capture significant changes in the organization and size of included wards.

NOIS and NOIS-POSI are surveillance systems where numerators and denominators are registered. From these systems, it is sufficient to receive the results for each ward in the form of the proportion of patients with different types of infections.

From NPR, we will apply for data for all hospitalized patients at both intervention and control wards from and including 1. January 2020 up to the time of application in 2024, giving numerators and denominators for the periods before, during and after the intervention.

When comparing intervention and control groups, we will estimate relative risk (RR) and absolute risk difference (ARF) with 95% confidence intervals (table 2). We will report two-sided p-values where applicable and use the significance criterion p<0.05.

We will use modified Poisson regression to compare hand hygiene compliance one year after NOST was introduced in the intervention wards³. We will adjust for the factor used in stratification (hospitals) as a fixed effect.

Compliance will be analyzed and reported for each occupational group and total for all healthcare personnel. Outbreaks will be analyzed and reported as the number of outbreaks and secondary attack rate per arm, in total and distributed by patients and staff. The incidence of infection in patients will be analyzed and reported in total and by types of infection.

A more detailed description of the analyzes of the main and secondary outcomes will be published in a separate analysis plan.

[figure not shown]

Figure 1. Overview and schedule for the intervention and measurements in the evaluation

Table 2. Dummy table with results for compliance with hand hygiene recommendations

	Intervention arm	Control arm	ICC	Adjusted RR (95% CI)	ARF (95% KI)	p-value
Primary outcome						

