Compliance hand hygiene	540/900 ¹ (0.60)	369/900¹ (0.41)	0.020	1.683 (1.654 – 1.713)	0.279 (0.270-0.288)	<0.05

¹Number of hand hygiene performed by indicated events

Sample size

Sample size calculation (number of wards needed in each arm) is based on the following:

- Type I error rate: 0.05
- Power: 0.80
- Primary outcome is dichotomous with expected baseline proportion: 0.40
- Outcome is measured as simple difference at the end of the intervention period
- Intraclass correlation coefficient (ICC) of primary outcome: 0.10
- Expected number of measured events per cluster (hospital ward): 30
- Degrees of freedom used when adjusting for cluster-level covariates in the analysis: 2
- A priori stratification in the design and analyses
- Hypothesized intervention effect (increased proportion of compliance): 0.20

The estimation of necessary number of wards in both arms is conducted in parallel cluster-randomized trials calculator published by the National Institutes of Health (https://researchmethodsresources.nih.gov/grt-calculator).

Table 3 shows the function of the number of clusters (wards) per arm, and the number of events measured in each ward. The first row shows the number of clusters, while the first column shows the number of events measured per ward. The inner cells show the magnitude of the difference (increase in proportion) that we can identify as significant with a power of 80%. We assume that we

can detect a difference of at least 20%, and the calculations show that we have enough power for this if we have 26 wards in each arm, if there are 30 hand hygiene sessions measured in each ward.

Table 3. Detectable difference in the arms, distributed by number of participating wards per arm and number of events measured per ward

Absolute Detectable Difference Clusters (wards) per arm

		24	25	26	27	28
Events measured per ward	15	0,2266	0,2219	0,2175	0,2134	0,2094
	23	0,2113	0,2069	0,2028	0,199	0,1953
	30	0,2042	0,2	0,1961	0,1923	0,1888
	38	0,1992	0,1951	0,1912	0,1876	0,1841
	45	0,1962	0,1922	0,1884	0,1848	0,1814

Group allocation

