In this project, we will not register or collect direct identifiable personal data. In the hand hygiene observations, only the events and occupation are recorded, but not personal data on the people observed. Furthermore, we will only ask for statistics from VESUV and NOIS/NOIS-POSI. This data will include the number of people infected in outbreaks per ward distributed by employees and inpatients, as well as the number of inpatients with relevant types of infection in the surveillance of HAI. These data are regularly published at the hospital level. We will apply for data from NPR that includes information on each patient admitted to the relevant wards in the period from 1 January 2022 to mid-2024. However, we will ask for data without directly personally identifiable information (data without name and social security number).

Together with the data protection officer at NIPH, we will perform a data protection impact assessment (DPIA) related to the collection and handling of data in the project.

References

- 3. Zou G. A modified poisson regression approach to prospective studies with binary data. *Am J Epidemiol* 2004; **159**(7): 702-6.

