≥0.05	No	 The magnitude of the effect of being randomized and adhering to NOST is not sensitive to modelling assumptions. The direction of the effect of being randomized and adhering to NOST is not sensitive to modelling assumptions.

¹ Note that, in Stata, use of SUE requires that clustering within hospital be specified as an option to **suest** rather than **binreg** for all models, and that the variance-covariance matrix of the estimates (VCE) be computed using the observed, rather than the expected, information matrix (i.e., using the **vce (oim)** option of **binreg**).

9.2 Mean Difference Estimation 438

439 If fewer than 5% of wards do not adhere to their randomized treatment, we will estimate marginal 440 differences in means using linear regression with cluster-robust standard errors, with hospital as the cluster variable: 441

442 443

449

452

453

459

461 462

463

466

444 where for the bed days per inpatient stay outcome, y_i is bed days per inpatient stay for the *i*th hospital 445 446 ward, β_0 estimates the mean for controls, x_i indicates if the *i*th hospital ward was randomized to NOST, β_x estimates the effect of being randomized to NOST as a marginal mean difference, and σ is 447 448 the residual standard deviation.

 $y_i \sim N(\beta_0 + \beta_X x_i, \sigma)$

450 If 5% or more wards do fully not adhere to their randomized treatment, we will estimate marginal 451 differences in means using the model:

 $y_i \sim N(\beta_0 + \beta_X x_i + \beta_A a_i, \sigma)$

454 455 where $0 \le a_i \le 1$ models the degree of adherence by the *i*th hospital ward to NOST (see section 7.6 and the definition of a_i in section 9.1) and β_A estimates the effect of full adherence to NOST. The 456 457 marginal mean difference of being randomized to and adhering to NOST is estimated by $\beta_X + \beta_A$. We will use the same strategy for handling possible nonconvergence as described in section 9.1. 458

460 Estimation can be performed using Stata as follows:

```
regress bed i.treat c.adh, vce(cluster hospital)
```

464 where data are arranged with one ward per row, bed is a variable containing bed days per inpatient 465 stay, and the other variables are defined as in section 9.1.

467 Estimation can be performed using R as follows:

468

469

model = glm(bed ~ treat + adh, data = df, family = gaussian(link = "identity") coeftest(df, vcov. = vcovCL(model, cluster = hospital)

471 472

470

473 9.2.1 Sensitivity analysis

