Estimand The risk of postoperative site infection, measured over one year in periods of incidence surveillance of patients undergoing certain surgical procedures, in Norwegian hospital wards if NOST was introduced and adhered to versus if NOST was not introduced and not adhered to.
 Target population Inpatients undergoing surgical procedures monitored in NOIS-POSI groups (included in the NOIS-POSI surveillance)
 Outcome Variable Inpatient postoperative site infection (NOIS-POSI)
 ICE Strategy See sections 7.6, 9.1, and 9.1.1
 Effect Measure(s) RR and indicative RD

robust standard errors

490 10.2.7 Inpatient HAI Diagnosis (NPR)

Objective To assess the effect of NOST with respect to inpatient HAI diagnosis.		
Estimand The risk of inpatient HAI diagnosis, measured over one year, in Norwegian hospital wards		
if NOST was introduced and adhered to versus if NOST was not introduced and not adhered to.		
Target population Inpatients	Analysis set All	
Outcome Variable Inpatient HAI diagnosis (NPR)		
ICE Strategy See sections 7.6, 9.1, and 9.1.1	Missing Data Strategy See section 7.5	
Effect Measure(s) RR and indicative RD	Estimator Binomial regression with cluster-	
	robust standard errors	

491 10.2.8 Bed-days per Inpatient per Stay (NPR)

Objective To assess the effect of NOST with respect to bed-days per inpatient per stay.Estimand The mean number of bed-days per inpatient per stay, measured over one year, in
Norwegian hospital wards if NOST was introduced and adhered to versus if NOST was not
introduced and not adhered to.Target population InpatientsAnalysis set AllOutcome Variable Bed-days per stay (NPR)
ICE Strategy See sections 7.6, 9.2, and 9.2.1Missing Data Strategy See section 7.5
Estimator Linear regression with cluster-robust
standard errors

492 **11 Reporting Conventions**

In general, percentages in the table of baseline characteristics will be rounded to whole numbers, andsummaries of continuous variables will be presented to one decimal place.

495

496 Statistical estimates will be presented as points with two-sided 95% confidence intervals and *p*-values.

497 Point estimates and confidence intervals will be reported to 2 decimal places, and *p*-values will be 498 reported to three decimal places or as p < 0.001.

499 **12** Quality Assurance of Statistical Programming

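### The SAP models for NPR infection and length of stay leave out the pre-NOST ward data the protocol plans to obtain, and the length-of-stay target (ward average or per stay) is not stated

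*SAP*

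**What the plan says.** **Data planned.** Protocol, Data collection and outcomes, plans an NPR request covering all inpatients in both arms from 1 January 2020 into 2024, "giving numerators and denominators for the periods before, during and after the intervention". Protocol, Ethics, describes the same request as patient-level data "in the period from 1 January 2022 to mid-2024". Protocol, Introduction, puts implementation in the first quarter of 2023, but also says that training and implementation began in hospitals in autumn 2022.

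**Models planned.** SAP 5.2 measures all secondary outcomes over the trial year only and aggregates them by ward. SAP 9.1 (binomial regression, used for HAI diagnosis) and SAP 9.2 (linear regression for bed-days) contain arm and, if 5% or more of wards do not fully adhere, an adherence term. The bed-days command is "regress bed i.treat c.adh, vce(cluster hospital", with one row per ward and no weight. SAP 7.2 mentions covariate columns, but SAP 7.3 names only subgroup variables. Hospital enters only through the standard errors.

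**Length-of-stay estimand.** SAP 10.2.8 states it as "The mean number of bed-days per inpatient per stay, measured over one year", in Norwegian hospital wards, with inpatients as target population. Protocol Table 1 gives hospital stays as the denominator.

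**The concern.** The departments named in the SAP include psychiatry, orthopaedics, neurology and oncology. Such wards can be expected to differ in usual length of stay and infection risk for reasons unrelated to NOST. In a ward-level comparison those stable differences sit in the residual variance, although the planned registry request would measure them before NOST began. At stake is the width of the confidence intervals for two of the eight secondary outcomes, both serving the protocol's second objective.

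A separate question is what the bed-days coefficient estimates. An unweighted regression on ward means contrasts the average ward in each arm. A mean per stay over inpatients gives larger wards more weight. The SAP does not say which is meant. SAP 9.1 raises no such question, because binomial regression on counts already weights wards by their number of inpatients.

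**Working it through.** **1. The plan's own figure.** The documents give a sample size for the primary outcome only, and none for the NPR outcomes. Inputs (Protocol, Sample size): "Type I error rate: 0.05", taken as two-sided; power 0.80; "Primary outcome is dichotomous with expected baseline proportion: 0.40"; "Hypothesized intervention effect (increased proportion of compliance): 0.20"; ICC 0.10; 30 events per ward.

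- Per arm before clustering: [1.96 × √(2 × 0.5 × 0.5) + 0.842 × √(0.24 + 0.24)]² / 0.20² = 97.
- Design effect: 1 + 29 × 0.10 = 3.9.
- Wards per arm: 97 × 3.9 / 30 = 12.6, against the stated 26.

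The stated figure is therefore not reproduced by the standard formula. Protocol Table 3 is matched (to 0.0001) only if the variance is doubled and the degrees of freedom are 2(2g − 1) − 2, for g wards per arm, which may reflect an undocumented calculator setting. This errs on the conservative side, concerns the primary outcome and does not bear on the present point. Below, 26 wards per arm serves only as a yardstick.

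**2. Baseline adjustment of bed-days, equal ward weights.** Let ρ be the correlation between a ward's pre-NOST and trial-year mean stay. The documents give no value, so a range is assumed. Residual variance after adjustment is 1 − ρ² of the unadjusted value. The detectable difference in ward-SD units is (1.96 + 0.842) × √(2(1 − ρ²)/26); unadjusted it is 0.777.

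| Assumed ρ | Variance left | SE factor | Detectable difference (ward-SD) | Unadjusted wards per arm for the same precision as 26 adjusted |
|---|---|---|---|---|
| 0.3 | 0.91 | 0.954 | 0.741 | 28.6 |
| 0.5 | 0.75 | 0.866 | 0.673 | 34.7 |
| 0.7 | 0.51 | 0.714 | 0.555 | 51.0 |
| 0.8 | 0.36 | 0.600 | 0.466 | 72.2 |
| 0.9 | 0.19 | 0.436 | 0.339 | 136.8 |

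A simulation of 52 wards (13 hospitals with 4 wards each, no hospital effect, 4,000 runs) gave variance ratios of 0.73, 0.37 and 0.19 at ρ = 0.5, 0.8 and 0.9, in line with the formula.

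**3. HAI diagnosis.** The factor 1 − ρ² is a linear-model result, while SAP 9.1 uses a log link on counts. Sampling noise in infection counts lowers the year-to-year correlation. No figure is offered. Log prior risk is undefined for a ward with no prior infection: with an assumed 200 inpatients and 1% risk, the chance of none is 0.99²⁰⁰ = 0.13.

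**4. Weighting of bed-days.** The target can matter. Suppose half the wards have 400 stays and no effect, and half have 1,600 stays and an effect of −0.4 day.

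- Equal weights: (0 − 0.4)/2 = −0.20 day.
- Per stay: (400 × 0 − 1,600 × 0.4)/2,000 = −0.32 day.

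With a common effect in all wards the two agree.

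Stay weighting also has a variance cost. With an assumed mean of 1,000 stays per ward and a ward-size coefficient of variation of 0.6, its variance relative to equal weighting is 0.74, 1.00, 1.29 and 1.34 at an ICC of 0, 0.001, 0.01 and 0.05. In the simulation, stay weighting combined with baseline adjustment left 0.99, 0.51 and 0.26 of the planned model's variance at ρ = 0.5, 0.8 and 0.9.

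**5. Baseline window.** Counting to the start of 2023, the Methods date gives three pre-NOST years and the Ethics date gives one. If any randomised ward began in autumn 2022, the Ethics date leaves it less than twelve months.

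**The case against.** The strongest reply is that nothing here is wrong in the sense of bias. Randomisation protects the unadjusted comparison, the documents set no power target for these outcomes, and Protocol, Group allocation, expects several hundred wards. All of that stands. The adjustment is a cheap improvement, not a repair of an invalid analysis, and no precision shortfall has been shown.

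The size of the gain is also open. At ρ of 0.3 to 0.5 the variance falls by only 9% to 25%. Because wards are randomised within hospital and standard errors are clustered by hospital, the relevant correlation is largely the one between wards of the same hospital, which the documents do not give either.

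Four stronger readings are tempting and are not supported:

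- *Equal weighting wastes precision.* If stable ward differences dominate, equal weights are near-optimal and stay weighting raises the variance.
- *The bed-days analysis misses its estimand.* SAP 5.2 declares ward-level aggregation and SAP 10.2.8 refers to hospital wards, so the wording is ambiguous, and the two targets differ only if the effect varies with ward size.
- *The 2 degrees of freedom in the sample size show that covariates were dropped from these models.* That allowance belongs to the primary-outcome calculation.
- *The data are in hand.* The protocol says they will be applied for, and ethics approval for their use is still to be sought.

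The SAP's reason for dropping hospital fixed effects, too many parameters, does not carry over: one baseline covariate costs one parameter.

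**Conclusion.** The point holds as a worthwhile, low-cost improvement to two secondary analyses. The protocol plans to obtain pre-NOST ward data on both NPR outcomes, and the SAP models do not use them. For bed-days with equal ward weights, the variance left after adjustment runs from 0.91 to 0.19 of the planned value over assumed correlations of 0.3 to 0.9. A reader might infer that the loss is certainly large; the documents give no correlation and so cannot show that. For HAI diagnosis the direction is the same, but the size is unknown and probably smaller.

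The two NPR start dates contradict each other and must be reconciled, although both precede the planned 2023 start. The weighting question is one of stating the target. It should not be presented as a gain in precision or as proof that the planned estimate is wrong.

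**What to change.** 1. In SAP 7.3, 9.1 and 9.2, prespecify one ward-level pre-randomisation covariate per NPR outcome: prior mean stay for bed-days, and prior HAI risk (on the log scale) for HAI diagnosis. State the baseline period, a rule for zero counts such as adding 0.5 before taking logs, and a fallback for new or merged wards, for example the hospital-by-department mean. Keep the unadjusted model as sensitivity.
2. Reconcile the NPR start date between the protocol's Data collection and Ethics sections, so that a full pre-NOST baseline period is covered for every ward.
3. In SAP 10.2.8, state whether the target is the ward average or the per-stay mean, align SAP 9.2 with it, and report the other weighting as sensitivity. If stays are counted over the trial year, note that this weight is itself measured after randomisation.

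The cost is SAP wording, a few derived columns and a small amount of extra analysis, all dependent on the NPR application being granted. The change should be made before unblinding: SAP 4.4 has the secondary analyses run unblinded, and a covariate or weight chosen then could look data-driven.

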The primary outcome is compliance with hand hygiene recommendations by hospital employees who do patient-related work. Compliance will be assessed one year after randomization by trained and experienced observers. The observers will record the number of observations made and the number of these observations that meet the criteria for compliance. The number of observations and compliances will be measured at the level of hospital ward. Compliance will therefore be aggregated at the level of hospital ward and the primary outcome is a count variable.

161 **5.2 Secondary outcomes**

As for the primary outcome, all secondary outcomes will be aggregated at the level of hospital ward.
Unlike the primary outcome, all secondary outcomes are measured over the one-year trial period
rather than at the end of the trial.

165

Sec	ondary Outcome	Туре	Denominator	Data source			
Infe	Infectious disease outbreaks						
1.	Outbreak	Count	Wards	VESUV			
2.	Inpatient infection	Count	Inpatients in wards with outbreaks				
3.	Employee infection	Count	Employees in wards with outbreaks				
Sur	veillance of HAI						
4.	Inpatient infection	Count	Inpatients included in	NOIS			
			the surveillance				
5.	Inpatient antibiotic treatment	Count	Inpatients included in				
			the surveillance				
Sur	veillance of postoperative site infectior	15					
6.	Inpatient treatment for postoperative	Count	Surgical inpatients	NOIS-POSI			
	site infection		included in the				
			surveillance				
HAI	diagnoses						
7.	Inpatient HAI diagnosis	Count	Inpatients in the study period	NPR			
Len	gth of hospital stay						
8.	Bed-days per inpatient per stay	Continuous		NPR			

166 167

168 6 Sample Size

169 Assuming $\alpha = 0.05$, $\beta = 0.8$, a control risk of 0.4, an intervention risk of 0.6 (i.e., the treatment effect 170 is a risk difference of at least 0.2), an ICC of 0.1, an average cluster size of 30 observations among 171 hospital employees who do patient-related work, a loss of 2 d.f. for adjustment of cluster-level 172 covariates, and stratification by hospital, it was estimated that at least 52 hospital wards should be 173 recruited (26 in each arm).

7 General Analysis Considerations

175 **7.1 Timing of Analyses**

176 Analyses will be performed after the database is locked. No interim or follow-up analyses are planned.

177 7.2 Analysis Sets

Although this SAP defines three populations, there is only a single analysis set that will contain all

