474 We will perform sensitivity analyses similar to those for risk ratios (see section 9.1.1).

10 Estimands 475

476 This section presents all estimands in terms of the objective, a statement of the estimand in plain 477 language, the target population (i.e., who or what the estimate can be applied to), the analysis set 478 (i.e., what subset, if any, of the full analysis set will be used to perform the analysis), the outcome 479 variable, strategies for handling ICEs and missing data, the effect measure that will be estimated, and 480 the estimator used to perform the analysis.

481 **10.1 Primary Outcome Estimand**

Objective To assess the effect of NOST with respect to compliance with hand hygiene recommendations.

Estimand The risk of compliance with hand hygiene recommendations, measured at one year, by employees who perform patient-related work in Norwegian hospitals if NOST was introduced and

SAP version: 1.1

adhered to versus if NOST was not introduced and not adhered to.			
Target population Employees	Analysis set All		
Outcome Variable Compliance with hand hygiene recommendations			
ICE Strategy See sections 7.6, 9.1, and 9.1.1	Missing Data Strategy See section 7.5		
Effect Measure(s) RR and indicative RD	Estimator Binomial regression with cluster-		
	robust standard errors		

483 **10.2 Secondary Outcome Estimands**

484 **10.2.1 Outbreaks (VESUV)**

Objective To assess the effect of NOST with respe	ct to outbreaks.	
Estimand The risk of outbreak, measured over one year, in Norwegian hospital wards if NOST was		
introduced and adhered to versus if NOST was not introduced and not adhered to.		
Target population Hospital wards	Analysis set All	
Outcome Variable Outbreaks (VESUV)		
ICE Strategy See sections 7.6, 9.1, and 9.1.1	Missing Data Strategy See section 7.5	
Effect Measure(s) RR and indicative RD	Estimator Binomial regression with cluster-	
	robust standard errors	

485 **10.2.2 Inpatient Infection (VESUV)**

Objective To assess the effect of NOST with respe	ct to inpatient infection (using data from VESUV).		
Estimand The risk of inpatient infection defined as part of an outbreak, measured over one year, in			
Norwegian hospital wards if NOST was introduced and adhered to versus if NOST was not			
introduced and not adhered to.			
Target population Inpatients	Analysis set Wards with reported outbreak		
Outcome Variable Inpatient infections (VESUV)			
ICE Strategy See sections 7.6, 9.1, and 9.1.1	Missing Data Strategy See section 7.5		

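### SAP 10.2.2 and 10.2.3 define outbreak-related infection risk for hospital wards in general but compare the arms only in wards that had an outbreak after randomisation

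*SAP*

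**What the plan says.** **Estimand.** SAP 10.2.2 describes its target as "The risk of inpatient infection defined as part of an outbreak, measured over one year, in" Norwegian hospital wards, contrasting NOST introduced and adhered to with NOST not introduced. SAP 10.2.3 does the same for employees. Neither sentence limits the target to wards that have an outbreak.

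**Analysis set and denominators.** Both entries give "Analysis set Wards with reported outbreak". The outcome table in SAP 5.2 uses matching denominators: "Inpatients in wards with outbreaks" for outcome 2 and "Employees in wards with outbreaks" for outcome 3.

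**Timing.** SAP 5.2 states that "all secondary outcomes are measured over the one-year trial period". Whether a ward has an outbreak is thus settled after randomisation. It is also an outcome in its own right: the estimand in SAP 10.2.1 opens "The risk of outbreak, measured over one year, in Norwegian hospital wards if NOST was" introduced, and that analysis uses all wards.

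**Effect measure.** Both entries call for a risk ratio and an indicative risk difference between arms. The results table in SAP section 8 has columns for confidence intervals and a p-value.

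**Protocol.** Table 1 lists a secondary attack rate for inpatients and staff, and the text under Data collection and outcomes reports it per arm beside the number of outbreaks. The same section obtains inpatients per ward per day from NPR and asks hospitals to "submit the number of full-time positions per included ward".

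**The concern.** NOST may change which wards have an outbreak; the trial asks that question directly in SAP 3.2 and as outcome 1. Keeping only outbreak wards therefore selects on a possible effect of treatment. Two things follow.

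- A ward where NOST prevents an outbreak leaves the analysis instead of contributing zero cases. The benefit that the estimand sentence asks about is removed by construction, with no further assumption needed.
- The remaining wards in the two arms need not be alike. If the outbreaks that still occur under NOST are a different mix (larger or smaller) from those in control wards, the risk ratio mixes that difference with any effect on spread.

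At stake is what the published risk ratios and p-values for outcomes 2 and 3 can be taken to mean. For employees this matters more, because no other outcome in SAP 5.2 counts infections in staff.

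**Working it through.** **Figures in the plan.** The documents give no outbreak risk, attack rate or power figure for these outcomes, so there is none to reproduce. All rates below are assumptions. The only design figures used are the minimum of 26 wards per arm (SAP section 6) and, for scale, 150 per arm as one reading of the several hundred wards expected in the protocol.

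**Formula.** Let p be the proportion of wards with an outbreak and s the average proportion infected in those wards, with subscripts N (NOST) and C (control). Assume equal ward sizes and denominators on the same basis.

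- Planned RR = s_N / s_C
- All-ward RR = (p_N × s_N) / (p_C × s_C) = outbreak RR × planned RR

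The planned analysis estimates only the second factor. The two agree when NOST leaves outbreaks unchanged (outbreak RR = 1).

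**Illustrations with p_C = 10% and p_N = 5%** (outbreak RR 0.50). In the second and third rows, half the control outbreaks are small (10% infected) and half large (30% infected), so s_C = 20%.

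| Assumed pattern | s_C | s_N | All-ward RR | Planned RR |
|---|---|---|---|---|
| Same attack rate in both arms | 20% | 20% | (0.05 × 0.20)/(0.10 × 0.20) = 0.50 | 0.20/0.20 = 1.00 |
| NOST prevents only small outbreaks | 20% | 30% | (0.05 × 0.30)/(0.10 × 0.20) = 0.75 | 0.30/0.20 = 1.50 |
| NOST prevents only large outbreaks | 20% | 10% | (0.05 × 0.10)/(0.10 × 0.20) = 0.25 | 0.10/0.20 = 0.50 |

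**Range.** With the attack rate unchanged, the planned RR is 1.00 whatever the control outbreak risk, while the all-ward RR is 0.50 if NOST halves outbreaks and 0.75 if it cuts them by a quarter. If NOST also cuts the attack rate by 20%, the planned RR is 0.80 and the all-ward RR 0.50 × 0.80 = 0.40 or 0.75 × 0.80 = 0.60.

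**A less extreme mix.** Let half the wards be low-spread (5% infected in an outbreak) and half high-spread (15%), with outbreak risk 0.30 in both under control. NOST halves outbreaks in the low-spread wards only.

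- s_C = (0.30 × 0.05 + 0.30 × 0.15)/0.60 = 0.100
- s_N = (0.15 × 0.05 + 0.30 × 0.15)/0.45 = 0.117
- Planned RR = 0.117/0.100 = 1.17
- All-ward RR = (0.15 × 0.05 + 0.30 × 0.15)/(0.30 × 0.05 + 0.30 × 0.15) = 0.0525/0.060 = 0.875

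**Wards left in the planned analysis at 10% v 5%.** With 26 per arm: 26 × 0.10 = 2.6 and 26 × 0.05 = 1.3, about 4 in total. With 150 per arm: 15 and 7.5, about 22. With 26 per arm, the chance that at least one arm has no outbreak is 1 − (1 − 0.95^26)(1 − 0.90^26) = 0.31, and the log RR then cannot be estimated. Sparse events of this kind would affect an all-ward RR as well, so this shows how little information there is and does not by itself argue against the restriction.

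**The case against.** **The protocol chose this measure.** A secondary attack rate is conditional on an outbreak by definition, and the protocol's Study populations section places its secondary cases within outbreak periods. Read as an attack-rate ratio, 1.00 is the right answer in the first illustration. This stands: the attack rate is a legitimate description, and the SAP denominators carry it over. It does not rescue the SAP, which attaches to it an unconditional estimand and a risk ratio between randomised arms. Rewording the estimand as conditional would remove the mismatch but leave the selection problem.

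**Prevented outbreaks are not lost to the trial.** A reader might infer that the trial cannot detect this benefit at all. The documents do not support that. Outcome 1 compares outbreaks in all wards, and the NOIS infection and NPR diagnosis outcomes also have all wards as their analysis set. In the first illustration, outcome 1 would show 0.50 beside the attack-rate ratio of 1.00.

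**The SAP might seem to contradict itself.** SAP 7.2 says "there is only a single analysis set that will contain all" randomised, non-excluded wards, which could be read as ruling out the restriction. The opening of SAP section 10 explains that the analysis-set field names any subset of that full set. The two can be read together, and no contradiction is claimed here.

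**The analysis might seem bound to show harm.** It is not. Apparent harm needs the prevented outbreaks to be mainly the smaller or lower-spread ones. In the opposite case both ratios point towards benefit (0.25 and 0.50). The selection bias can run either way, and its size cannot be known from the documents.

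**Counting zeros has its own risk.** SAP 7.5 treats wards that never or only intermittently report as missing data, so a blanket zero could turn non-reporting into absence of infection. This stands and shapes the fix.

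**Conclusion.** The concern holds for SAP 10.2.2 and 10.2.3. The stated estimand is an all-ward risk; the planned RR is an attack-rate ratio in wards selected after randomisation. The omission of prevented infections follows from the definition whenever NOST changes the outbreak risk: the planned RR differs from the all-ward RR by a factor equal to the outbreak RR (given equal ward sizes and the same denominator basis). In the three assumed patterns with outbreaks halved, that is a factor of two. Bias in the attack-rate comparison itself further requires outbreak wards to differ between arms, which is plausible but not shown by the documents.

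Severity is moderate. Two of eight secondary outcomes are affected; the primary outcome, the sample size and the other six secondary outcomes are not.

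**What to change.** - In SAP 10.2.2 and 10.2.3, base the between-arm RR on all randomised, non-excluded wards. Change the denominators of outcomes 2 and 3 in SAP 5.2 to all inpatients (NPR) and to full-time positions per ward, stating that positions are a proxy for the number of employees.
- Count zero cases for wards with no notified outbreak, on the same basis as outcome 1. State a rule that separates these from wards known not to report, and handle the latter under SAP 7.5.
- Keep the protocol's secondary attack rate in outbreak wards as a descriptive result per arm, without a p-value or causal wording, and present it beside outcome 1.

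**Cost.** No new data are needed, since the protocol already plans to obtain inpatients per ward from NPR and positions for every included ward. The change is a small departure from protocol Table 1, to be reported and justified under SAP 8.2. It should be made before unblinding, because SAP 4.4 has the secondary analyses run unblinded and a later change of analysis set would be hard to defend. The all-ward RR will still be imprecise if outbreaks are few.
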